17. STATISTICAL CONSIDERATIONS

Sample size

In UK primary care (Clinical Practice Research Datalink), patients with relapsing PMR had a mean cumulative prednisolone dose of 5g over 18 months (coefficient of variation (CV) 0.78) (68).

A clinically relevant reduction is benchmarked against the reduction likely to substantively reduce the risk of fracture or infection. Extrapolating from observational data, an average reduction in cumulative prednisolone dose of 1.5g (a reduction in mean daily dose of 2.7mg over 18 months) would be predicted to significantly reduce hip and vertebral fracture risk (69). This corresponds to a 30% reduction in cumulative dose. Our PPI group helped inform this target effect size: discussions around trade-offs revealed that most would not consider a DMARD worth it unless it could substitute for more than 2.5mg daily prednisolone over an 18-month period.

Assuming a log-normal distribution, 200 participants will provide 90% power to detect a target 30% reduction in cumulative prednisolone dose, assuming a CV of 0.78, 2-sided independent t-test for fold change (H0: mean fold change=1), 5% significance and 20% attrition (24) (nQuery v3.0). The trial will retain at least 80% power if the CV is as large as 0.94.

As part of this Australia is recruiting 50 participants there for 25% of the total number for the study.

Planned recruitment rate

Recruitment from secondary care: there will be 3 sites. Each site is expected to be open and recruiting participants over a 12-month period.

We estimate a 3:1 screen: recruitment ratio as being realistic. From the PCRN route plus referrals from rheumatologists, GPs and self- referrals, it is estimated that 150 participants will attend screening visits and 50 will be randomised in Australia.

18. STATISTICAL ANALYSIS

18.1 GENERAL CONSIDERATIONS

A full statistical analysis plan (SAP) will be in place prior to any comparative analyses according to guidelines (70) The statistical analysis is the responsibility of the CTRU Statistician and will not include the economic evaluation (section 16). All analyses and patient populations will be predefined in the SAP.

The intention to treat (ITT) population will include all randomised patients, to be analysed in groups assigned at randomisation. A per-protocol population will be defined accounting for major protocol deviations, relating to intervention compliance, eligibility and other criteria agreed by the Trial Management Group prior to any unblinded efficacy analyses. Participants in the Per-Protocol population will be analysed according to randomised allocation.

Primary analysis will be conducted on the intention-to-treat (ITT) population; a secondary per-protocol population analysis will also be undertaken. Statistical monitoring of safety data and underlying assumptions of the statistical design will be conducted and reported to the Data Monitoring and Ethics Committee (DMEC) according to an agreed DMEC Charter.

At the time of the final analysis, the trial will be analysed and reported according to the CONSORT reporting standards (71).

18.2 ANALYSIS OF PRIMARY OUTCOME MEASURE

The primary analysis on log (cumulative prednisolone-equivalent dose reported over 18 months) will use multivariable linear regression, with covariates for the minimisation factors (listed in Section 11.3); age at randomisation will be retained as a continuous covariate, under transformation as necessary. Adjusted mean fold difference in cumulative prednisolone dose will be presented with 95% confidence interval (CI) and significance. Summaries on mean fold difference and absolute difference in cumulative prednisolone dose will be presented.

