8.1 INCLUSION CRITERIA FOR RANDOMISATION

Participants meeting ALL the following criteria will be considered for enrolment into the study

1. Age 18 years or more at the time the consent form is signed
2. ALL of:
 - (i) documented¹ diagnosis of PMR, confirmed by the local investigator.
 - (ii) previous steroid-responsive bilateral ache in the region of the trapezius, shoulder or upper arms.
 - (iii) previous C-reactive protein (CRP) greater than 5mg/L, or erythrocyte sedimentation rate (ESR)/plasma viscosity above local laboratory reference range, at either diagnosis or at time of a flare of PMR.
3. At least 4 points from a possible 6:
 - Previous stiffness in association with other features of PMR: **2 points**.
 - Previous aching of hip area (groin, buttock, lateral hip or upper thigh) in association with other features of PMR: **1 point**.
 - Rheumatoid factor (RF) and anti-citrullinated peptide antibody (ACPA/anti-CCP) both within local laboratory reference range at or during the 1 year prior to the screening visit: **2 points**.
 - No rheumatologist-documented hand or foot synovitis during active PMR symptoms: **1 point**.
4. Currently taking steroid treatment for PMR and willing to attempt dose reduction (tapering).

5. At least one previous relapse during steroid therapy, defined as steroid-responsive recurrence of PMR symptoms (aching in hip and/or shoulder areas).
6. Consent to participate.

8.2 EXCLUSION CRITERIA FOR RANDOMISATION:

Participants will be excluded from this study for ANY of the following reasons:

1. Contraindication to tapering steroid dose, or to methotrexate therapy²
2. Women who are currently pregnant, lactating or planning to become pregnant in the next 2 years
3. Women of child-bearing potential (WCBP) or men unwilling to use an effective birth control measure (Appendix 2) whilst receiving treatment (either methotrexate or leflunomide)
Women of child-bearing potential (WCBP) or men unwilling to use an effective birth control measure (Appendix 2) and for an appropriate period after the last dose of protocol treatment:(Six months in the case of methotrexate, applicable for both male participants and women of child-bearing potential (WCBP)). In the case of male participants, the contraceptive measures can be taken by either themselves or their female partners.

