11.3 RANDOMISATION

Randomisation will be a 1:1 allocation ratio to receive either Usual Care (steroid taper) Alone or Usual Care plus DMARD. Randomisation will be based on a minimisation algorithm with random component to ensure treatment groups are well-balanced for the following participant characteristics:

- site;
- number of previous relapses
- biological sex;
- prednisolone dose equivalent prior to last relapse (5mg or less, greater than 5mg) (see Appendix X for details of conversions from other glucocorticoids).

Randomisation process and timing

Participants who have previously been registered and have confirmation of eligibility will be randomised into the trial by an authorised member of the site research staff, as detailed on the Authorised Personnel Log. Randomisation will be performed centrally using the same CTRU automated web-based system as was used during registration and the same site code, authorisation code and PIN will be required. The baseline assessments and questionnaires should be completed BEFORE the participant is randomised.

The following information will be required whilst accessing the automated web-based system:

- site
- number of previous relapses
- biological sex
- prednisolone dose equivalent prior to last relapse (5mg or less, greater than 5mg)
- confirmation of participant's eligibility for the trial
- confirmation of informed consent
- confirmation of completion of baseline participant questionnaires

Web address for 24-hour randomisation: <https://lictr.leeds.ac.uk/webrand/>

Once randomisation is complete, the system will allocate a treatment arm for the participant and inform the user of the allocation.

The CTRU will send an automated email confirming participant randomisation and confirming the treatment allocation to the:

- site research team and
- site pharmacy

Site Research Team Post-Randomisation Activities

- Check automated email from CTRU to ensure participant information is correct e.g. initials, date of birth
- Update the participant's record on the STERLING Participant ID Log by adding details of the treatment allocation
- Return a copy of the completed participant contact details forms to CTRU

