14.5 BASELINE ASSESSMENTS (WEEK 0)

The baseline assessment should take place for all consenting, registered and eligible participants within 6 weeks of screening. The visit should take place in person. Prior to randomisation the assessments listed below

should be completed and documented on the Baseline Assessments eCRF.

- Participant reported current steroid use
- Relevant medical history
- Urea & Electrolytes (U&E) test
- Full blood count
- Liver function test
- HbA1C test
- CRP test
- ESR test
- Physical examination - MSK system including elevation of upper limbs, joint swelling/tenderness/limitation of movement, and vascular including temporal arteries
- Vital Signs – including, BP, heart rate, temperature
- Weight, hip and waist circumference
- PMR Activity Score (52), requiring:
 - CRP (as stated above).
 - VAS global assessment (physician) (0-10).
 - Number of minutes of morning stiffness.
 - Upper limb elevation / active shoulder abduction (EUL) graded as 0-3.

Participant pain VAS (0-10) (see section 14.10)

In addition, the participant must be given the Participant Baseline Questionnaire Booklet (See section 14.10) to complete before completing the randomisation event on the CTRU 24-hour randomisation system. Persons accessing the randomisation system will be required to confirm that all baseline assessments and questionnaires are complete before randomisation can be completed.

14.6 TELEPHONE ASSESSMENTS WEEK 4, 8, , 60 and 72

Participants will be periodically contacted by the site team via a telephone call to check adherence to the prescribed treatment, collect details of adverse events and any significant changes to medical history or other relevant factors that may affect the administration or dosing of DMARD. For participants in the usual care plus DMARD arm, potential dose escalation will be discussed during the call (see section 13.1.11 for MTX escalation or section 13.2.8).

The data listed below will be collected at this time point.

- Steroid and DMARD use
- (S)AE reporting (including Adverse Events related to glucocorticoid toxicity e.g. infection, diabetes, hypertension and fracture)
- State that DMARD monitoring test results, if applicable, have been reviewed and that the participant is ok to continue ongoing prescribing.
- Whether a 9am cortisol test has been advised and if so the date windows during which it is anticipated that it might be done.

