16 OUTCOME MEASURES

16.1 PRIMARY OUTCOME MEASURE

The primary outcome measure is mean participant reported cumulative prednisolone dose between randomisation and 18 months post-randomisation, reported by participants via a monthly questionnaire.

Where a participant receives an alternative steroid medication to prednisolone, the steroid dose will be converted to a “Prednisolone equivalent dose” prior to analysis.

Intercurrent events of interest are:

- Death – to be handled under a treatment policy strategy;
- Discontinuation of trial treatment (including crossover to other arm) – to be handled under a treatment policy strategy;

Although steroid diaries are a part of routine clinical care, we acknowledge a lack of data as to the accuracy of participant-completed steroid diaries as a means to track medication usage. We have identified only small-scale results, incompletely reported and for different populations, claiming that medication diaries have satisfactory test-retest reliability (62) and that comparable methods of medication use surveillance lead to similar reported adherence levels (63).

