18.3 ANALYSIS OF SECONDARY OUTCOME MEASURES

PMR symptom severity measures, PMR activity score, and Patient-reported quality of life measures over 18 months: analysis of PMR-IS domain scores, health-related quality of life (EQ-5D-5L Utility), PMR-Activity Score will use multivariable repeated measures linear regression adjusting for minimisation factors, baseline value, treatment group, baseline-by-time interaction (if appropriate), age, time, and time-by-treatment group interaction. Centre will be fitted as a random effect, if feasible and has a positive variance component. Time will be fitted as a continuous variable, and the estimated time-by-treatment interaction effect with 95% CI and significance will be presented.

Time to steroid cessation, Time to PMR relapse: time to event will be calculated and summarised using Kaplan-Meier estimates. Adjusted hazard ratios will be estimated using Cox proportional hazards regression or parametric alternative, with covariates for minimisation factors (fitting centre as a random effect, if feasible) age and treatment group, and reported with 95% CI.

Steroid free remission at week 80 post randomisation will be summarised by treatment group and overall.

Number of relapses over time: A multivariable negative binomial regression model will be used to explore the number of relapses reported over follow-up time with an offset term for time at risk, adjusting for minimisation factors, age and treatment group. Centre random effects will be explored, assuming a Gamma distribution. Adjusted difference in rate of relapse with 95% CI will be reported.

Cumulative prednisolone-equivalent dose prescribed: A multivariable linear regression model will be fitted to log (cumulative glucocorticoid dose), adjusting for minimisation factors (fitting centre as a random effect, if feasible) age and treatment group. Adjusted mean fold difference in cumulative glucocorticoid dose with 95% CI will be reported.

Safety: The number of adverse events of special interest related to PMR or trial treatment, serious adverse events and SUSARs, in number of unique patients, will be reported by treatment received (MTX/LEF/Both/Neither) and by severity.

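### The primary model leaves out the steroid dose at randomisation, which is already recorded and is where the cumulative outcome starts, so available precision is given up

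*Protocol*

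**What the plan says.** The primary outcome (Protocol section 16.1) is "mean participant reported cumulative prednisolone dose between randomisation and 18 months post-randomisation". Section 18.2 analyses its logarithm by "multivariable linear regression, with covariates for the minimisation factors (listed in Section 11.3); age at randomisation will be retained as a continuous covariate".

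Section 11.3 lists the minimisation factors as site, number of previous relapses, biological sex, and "prednisolone dose equivalent prior to last relapse (5mg or less, greater than 5mg"). The last of these is the only steroid-dose term in the model.

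The dose at entry is available. Section 14.5 lists "Participant reported current steroid use" among the assessments to be completed before randomisation, and the schedule in section 14.2 has a steroid use review at baseline. Section 3 says that at baseline each participant moves to trial prednisolone at the equivalent of the dose taken just before that visit. Section 8.1 requires current steroid treatment and willingness to taper, but sets no lower or upper limit on the dose.

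For the repeated-measures secondary outcomes, section 18.3 specifies "adjusting for minimisation factors, baseline value, treatment group, baseline-by-time interaction (if appropriate), age, time" and further terms. The section 18.3 model for cumulative dose prescribed has minimisation factors, age and treatment group, and no entry dose.

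**The concern.** Cumulative dose over 18 months is the area under a dosing curve that begins at the dose held at randomisation. With no limits on entry dose, that starting point can differ several-fold between participants. Section 5.2 describes initial treatment at 15-25 mg daily and, from 10 mg, reductions of 1 mg every one to two months, so differences at entry may take months to disappear.

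The minimisation factor is a weak substitute. It has two levels and refers to a time before the last relapse. Section 5.2 says that a relapse typically leads to a 2-5 mg re-escalation before the taper resumes, so two participants in the same stratum can enter on quite different doses.

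Two things are at stake. Variation in the outcome that entry dose could explain stays in the error term. And because minimisation does not target current dose, a chance difference between arms would not be corrected in the analysis.

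**Working it through.** **Inputs from Protocol section 17.** 200 participants, 20% attrition, two-sided 5% t-test on the log scale, target 30% reduction, CV 0.78, and a fallback CV of 0.94. Allocation is 1:1 (section 11.3).

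**Reproducing the plan's figures.**
- Log-scale SD = sqrt(ln(1 + CV²)), which is sqrt(ln(1.6084)) = 0.689 at CV 0.78 and sqrt(ln(1.8836)) = 0.796 at CV 0.94.
- Effect = ln(0.70) = -0.357.
- Evaluable = 200 × 0.80 = 160, or 80 per arm.
- Standard error (SE) of the log ratio = SD × sqrt(2/80): 0.689 × 0.158 = 0.109 at CV 0.78 and 0.796 × 0.158 = 0.126 at CV 0.94.
- Noncentral t power: 90.2% at CV 0.78 and 80.4% at CV 0.94. Both stated figures reproduce with no covariates at all.

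**Effect of adding baseline dose.** Let R² be the share of the remaining log-outcome variance that log baseline dose explains beyond the covariates already in the model. The residual SD becomes SD × sqrt(1 - R²). The protocol gives no value for R², so 10%, 20% and 40% are assumptions. Any gain from the existing covariates is ignored, as it is in the plan's own calculation.

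| R² (assumed) | Residual SD, CV 0.78 | Power, CV 0.78 | 95% CI around a ratio of 0.70, CV 0.78 | Power, CV 0.94 |
|---|---|---|---|---|
| 0 (as planned) | 0.689 | 90.2% | 0.56-0.87 | 80.4% |
| 10% | 0.654 | 92.9% | 0.57-0.86 | 84.4% |
| 20% | 0.617 | 95.3% | 0.58-0.85 | 88.3% |
| 40% | 0.534 | 98.7% | 0.59-0.83 | 95.3% |

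In sample-size terms the gain is 1/(1 - R²): 11%, 25% or 67% more participants.

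**Effect of a chance imbalance.** If the arms differ in log baseline dose by one standard error of that difference, the unadjusted log ratio moves by sqrt(R²) × SD × sqrt(2/80). At CV 0.78:
- R² 10%: 0.316 × 0.109 = 0.034, a factor of about 1.035.
- R² 20%: 0.447 × 0.109 = 0.049, a factor of about 1.05.
- R² 40%: 0.632 × 0.109 = 0.069, a factor of about 1.07.

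The ceiling, at R² = 100%, is 0.109, or about 11.5%. One could instead assume that baseline dose carries through in full proportion (a log-log slope of 1) with a log baseline SD of 0.8. That would need a variance of 0.64 out of a total of 0.475, an R² of 135%, which is impossible. The shift must therefore be tied to R², as above.

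**The case against.** The strongest reply is that nothing planned is missing. The sample size rests on an unadjusted t-test and meets its target, so adjustment would be a bonus on an adequate design. That is correct. The gain is real but unquantified in the documents, and only the part beyond the existing covariates counts. Number of relapses and dose before the last relapse carry some of the same information; at the low end of the assumed range the gain is under three percentage points of power at CV 0.78.

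A reader might infer that the omission biases the result, or that a chance imbalance is an error the analysis does not cover. Neither follows. Randomisation keeps the estimate unbiased across repetitions of the trial, and the unadjusted standard error already includes this source of variation.

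A reader might also see an inconsistency with the secondary models. It is not a contradiction. Their baseline value is the same measure taken at week 0, whereas cumulative dose is zero at randomisation and has no such counterpart. The comparison shows only that baseline adjustment is used elsewhere in the plan.

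It is tempting to ask for the same covariate in the steroid cessation and relapse models. The reasoning and arithmetic here concern cumulative dose and do not support that extension.

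Finally, section 18.1 leaves the predefinition of analyses to the SAP, which is not shown and might add the term. But section 18.2 names the covariates of the primary model, and a SAP that followed it would leave entry dose out.

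**Conclusion.** The point stands as a worthwhile improvement in efficiency, not as a design error. The protocol names a covariate set for its primary model that omits a variable it already collects and from which the outcome starts.

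The benefit matters most at the protocol's own pessimistic CV of 0.94, where power of 80.4% would become roughly 84%, 88% or 95% at an assumed R² of 10%, 20% or 40%. At CV 0.78 the rise is from 90.2% to roughly 93%, 95% or 99%. A one-standard-error imbalance moves the unadjusted ratio by about 3.5%, 5% or 7% at CV 0.78.

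The omission, and the fact that the variable is collected, can be read directly from the text. The size of the gain depends on the assumed R² and on the log-normal model of section 17.

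**What to change.** Amend section 18.2, and mirror it in the SAP, so that log(prednisolone-equivalent daily dose at randomisation) is a prespecified continuous covariate in the primary model. Keep the minimisation factors and age. Make the same change to the section 18.3 model for cumulative dose prescribed. Section 8.1 requires every participant to be taking steroid at entry, so the logarithm should be defined, and Appendix 1 already supplies the equivalences.

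Do this before any comparative analysis. If the term were added after an imbalance had been seen, it would look data-driven.

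The cost is one sentence in each document and one degree of freedom. No new data collection is needed, and the sample size does not change.

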18.3 ANALYSIS OF SECONDARY OUTCOME MEASURES

PMR symptom severity measures, PMR activity score, and Patient-reported quality of life measures over 18 months: analysis of PMR-IS domain scores, health-related quality of life (EQ-5D-5L Utility), PMR-Activity Score will use multivariable repeated measures linear regression adjusting for minimisation factors, baseline value, treatment group, baseline-by-time interaction (if appropriate), age, time, and time-by-treatment group interaction. Centre will be fitted as a random effect, if feasible and has a positive variance component. Time will be fitted as a continuous variable, and the estimated time-by-treatment interaction effect with 95% CI and significance will be presented.

Time to steroid cessation, Time to PMR relapse: time to event will be calculated and summarised using Kaplan-Meier estimates. Adjusted hazard ratios will be estimated using Cox proportional hazards regression or parametric alternative, with covariates for minimisation factors (fitting centre as a random effect, if feasible) age and treatment group, and reported with 95% CI.

Steroid free remission at week 80 post randomisation will be summarised by treatment group and overall.

Number of relapses over time: A multivariable negative binomial regression model will be used to explore the number of relapses reported over follow-up time with an offset term for time at risk, adjusting for minimisation factors, age and treatment group. Centre random effects will be explored, assuming a Gamma distribution. Adjusted difference in rate of relapse with 95% CI will be reported.

Cumulative prednisolone-equivalent dose prescribed: A multivariable linear regression model will be fitted to log (cumulative glucocorticoid dose), adjusting for minimisation factors (fitting centre as a random effect, if feasible) age and treatment group. Adjusted mean fold difference in cumulative glucocorticoid dose with 95% CI will be reported.

Safety: The number of adverse events of special interest related to PMR or trial treatment, serious adverse events and SUSARs, in number of unique patients, will be reported by treatment received (MTX/LEF/Both/Neither) and by severity.

Time to development of GCA will be summarised using Kaplan-Meier estimates. Adjusted hazard ratios will be estimated using Cox proportional hazards regression or parametric alternative, with covariates for minimisation factors (fitting centre as a random effect, if feasible) age and treatment group, and reported with 95% CI.

Adrenal insufficiency: The proportion of participants considered to be experiencing adrenal insufficiency will be reported in both groups.

Deaths: Number of deaths from all causes over 18 months post randomisation and time to death will be summarised by treatment received

